A. Screening: Post injury days 0-17

- Subjects admitted to the RSCIC with suspected complete SCI will be approached for participation shortly after admission. After providing informed consent, subjects will be screened between 0 and 17 days post injury. The screening will review of the medical record medical/surgical history and physical/neurological examination performed according to ISNCSCI guidelines to ensure an AIS Grade A SCI is present, or post-menopausal) and social or lifestyle factors that could alter ability to participate.
- A serum pregnancy test (for females of child bearing age).
- Standard of Care laboratory tests of kidney (TJUH Basic Metabolic Panel) and liver function (TJUH Hepatic Panel) will be reviewed to ensure the patient does not have a history of chronic liver or kidney failure, unknown to family or subject or not revealed on subject history interview.

- Serum calcium measurement. If initial serum calcium is <7.0 mg/dl, the subject will be given correctional calcium doses in accordance with standard hospital treatment protocol for subjects with critically low calcium levels. The subject may still be able to participate if the calcium level is corrected by the day prior to study drug infusion.
- Serum Vitamin D measurement. Subjects with initial vitamin D levels in the deficient range (<13ng/ml) will not be eligible for participation. If subject's 25-OH vitamin D is between 13 and 20, the subject will be supplemented with high potency oral ergocalciferol 50,000 International Units (IU) per week until retesting occurs at 4 weeks. At the time the screening value is returned, subjects with 25-OH vitamin D levels between 20 and 32 will be started on 2000 IU vitamin D daily and those with levels 32 and higher will be initiated on 1000 IU daily. Supplemental oral calcium of 1200 mg daily will be started on the same day as the vitamin D, except in cases of low values as described above.
- Intact Parathyroid Hormone (iPTH) measurement.

B. Baseline Assessments: Post-injury days 8-21

A Baseline Assessment will be completed between 8 and 21 days post-injury, and include the following:

- Completion of the World Health Organization (WHO) Fracture Risk Assessment Tool (FRAX)⁷³. The FRAX asks for information about age, date of birth, sex, weight, height, previous fracture history, parental fracture history, smoking, steroid use, history of rheumatoid arthritis, presence of a medical condition related to osteoporosis, alcohol use, and current hip bone mineral density (see data collection forms in Appendix B). All data are then entered into the FRAX website (available through the WHO) to obtain the 10 year probability of a fracture. No personal identifiers are used and no data is saved on the website.
- Collection of blood sample for pre-treatment levels of PINP as measures of bone formation, s-CTX as marker of bone resorption, IL-1 β as a pro-osteoclastogenic factor, CPK (Creatinine Phosphokinase) as a marker of muscle tissue and kidney function, and serum calcium. DXA scan, to be obtained as soon as the subject is medically stable for testing off the intensive/acute care floor (may be done up to 7 days after the infusion of study drug).

C. Study drug infusion: Post injury day 21

Within day 21 post injury, subjects will be administered study drug and assessed as follows:

- Measurement of serum calcium level to ensure therapeutic levels.
- A single IV infusion of ZA 5 mg or a placebo drug with the same dilution and duration of administration (prepared and dispensed by the TJUH IDS).
- The single IV infusion will be administered over a 2 hour period (2.5 mg per hour)
- Supplemental hydration as needed to keep urine output > 2000 cc per day from the day prior to study drug administration until 3 days post-infusion.
- Acetaminophen 650 mg every 4 hours for the 24 hour period following drug administration. This is intended to reduce the frequency and severity of fever or myalgias associated with ZA administration⁶¹.

D. Days 1-7, Post Drug Infusion

- After the first day, acetaminophen will continue to be offered as needed every 4 hours through day 3 post-infusion.
- Supplemental hydration will be continued as needed to keep urine output > 2000 cc per day until 3 days post-infusion
- Subjects will be assessed daily for 3 days, then weekly for one month after study drug administration for known side effects of the drugs, including myalgias, fever, gastrointestinal disturbances, and flu-like symptoms.

- Subjects will be assessed for participation in physical therapy and occupational therapy since receiving the study drug, as well as willingness to get study drug again via interview held 7 days following infusion.

E. Days 1, 3, 7, 14, Post-Drug Infusion

- Subjects will be assessed weekly for one month after study drug administration for known side effects of the drugs, including myalgias, fever, gastrointestinal disturbances, and flu-like symptoms.
- Laboratory values will be drawn for serum calcium, phosphate, and magnesium.

F. Month 1 Post Injury (+/-4 days)

- Subjects will be assessed weekly for one month after study drug administration for known side effects of the drugs, including myalgias, fever, gastrointestinal disturbances, and flu-like symptoms.
- Blood samples* for laboratory values will be drawn for s-CTX, IL-1 β , 25-OH vitamin D, serum calcium, intact parathyroid hormone, and Serum P1NP. *The total amount of blood drawn for all laboratory tests will be < 25 ml at each data collection session.

G. Month 2, 6 & 10 Post Injury

A patient questionnaire will be administered either in-person or by telephone. The questions cover:

- Any evidence or knowledge of bone fractures since the previous contact.
- Information about exercises and standing, including use of functional electrical stimulation (FES), such as how often and average daily duration.
- Supply of vitamin D and calcium tablets with reminder to bring pill bottles with them to clinic for follow up assessments and study sponsored refill of medications. At these follow up visits, pill counts will be done to assess their compliance with medication use.

H. Months 4 & 12 Post Injury

- Blood sample will be drawn for s-CTX, 25-OH vitamin D, serum calcium, intact parathyroid hormone. Serum P1NP will also be drawn at 4 months. The total amount of blood drawn for all laboratory tests will be < 25 ml at each data collection session.
- Complete neurological exam (at 12 months only)
- A patient questionnaire will be administered.
- DXA scan

I. Month 8 Post Injury

- Blood sample will be drawn for 25-OH vitamin D and serum calcium. The total amount of blood drawn for all laboratory tests will be < 25 ml at each data collection session.

J. Serum 25-OH Vitamin D Monitoring and Supplements

Since serum 25OH vitamin D represents a storage level of vitamin D accumulated over the preceding months, subjects with therapeutic values immediately after injury may have normal vitamin D stores which decline in subsequent months. For this reason, vitamin D levels in all subjects will be monitored not only at baseline but also at months 1, 4, 8 and 12. Subjects will be supplemented with 50,000 IU oral ergocalciferol weekly, if insufficient (serum level 13-20 ng/ml); 2000 IU cholecalciferol or ergocalciferol daily, if sub-therapeutic (serum vitamin D level 21-31ng/ml). Those subjects in the therapeutic range for serum 25-OH vitamin D will be given a maintenance dose of 1000 IU oral vitamin D daily.

Table 4: Study Events and Visit Schedule

	Screening (Day 0-17)	Baseline (Day 8-21)	Study Drug and Acetaminophen Administration (within 21 days of injury)	1 month + / - 4 days	4 months + / - 7 days	8 months + / - 14 days	1 year + / - 14 days
Medical History Standard Care	X						
Physical Exam Standard Care	X						
Basic Metabolic and Hepatic Panel) Standard Care	X						
FRAX Score		X					
Study Drug Infusion			X				
Acetaminophen Administration			X ^a X ^b				
Serum calcium, magnesium, phos Standard Care	X	X		X	X	X	X
Serum 25OH-D Standard Care	X			X	X	X	X
Serum iPTH ^d Study Specific	X			X	X		X
P1NP ^e Study Specific		X		X	X		
IL-1 beta ^f Study Specific		X		X			
Serum CTX ^g Study Specific		X		X	X		X
CPK ^h Study Specific		X					
DXA** Study Specific		X ^c			X		X

- a) Administered every 4 hours for the first 24 hours following study drug infusion
- b) Administered every 4 hours PRN through day 3 following study drug infusion
- c) To be obtained as soon as medically stable to undergo DXA testing
- d) iPTH Blood Test Intact parathyroid hormone
- e) P1NP Blood Test N-terminal propeptide of Type I collagen
- f) IL-1 beta Blood Test Interleukin 1 beta
- g) S-CTX Blood Test Serum carboxy-terminal telopeptide of type I collagen
- h) CPK Blood Test Creatinine Phosphokinase

Table 5 Schedule of follow up contacts for **Years 2 through 4** of the study.

	Year 1 Every 2 Months	Year 2 Month 6	Year 2 Month 12	Year 3 Month 6	Year 3 Month 12	Year 4 Month 6	Year 4 Month 12
Questions about fractures	X	X	X	X	X	X	X
Questions about Vitamin D/calcium supplements	X	X	X	X	X	X	X
Questions about exercise and other treatments	X	X	X	X	X	X	X

Questions about functional status	X	X	X	X	X	X	X
-----------------------------------	---	---	---	---	---	---	---

Information on Physical Examinations and Clinical Assessments

Objective Evaluations: To ensure the patient has a complete spinal cord injury (AIS Grade A), investigators will perform a complete neurological exam according to ISNCSCI guidelines as part of initial screening (days 2-17 post injury). A confirmatory exam will be conducted in the 24 hours prior to study drug delivery. At the end of the study when the patient returns for final laboratory tests and DXA scan, a repeat neurological examination will be performed.

Subjective reports: Interviews will be conducted with patients every 2 months during the first year, either in person if testing is scheduled, or by phone between testing sessions. The first phone call will occur 2 months from injury if the subject is not an inpatient or not available for in-person interview. During these interviews, subjects will be asked about any evidence or knowledge of bone fractures since the previous contact. We will obtain information about exercises and standing, (including use of FES), such as how often and average daily duration.

Follow up for Subsequent Years of Grant Cycle

During the subsequent years of the grant cycle, patients will be contacted every 6 months for information on fractures sustained in the prior 6 months. As part of the consent form, we will be requesting permission to receive x-ray reports of any bone fracture experienced and mechanism of injury between years 1 and 4 post injury and collect information on participation in standing, lower extremity exercise and functional electrical stimulation (FES), and current calcium and vitamin D use.

[figure not shown]
Early Termination

Should a subject gain neurological function prior to initial drug administration and no longer have a complete SCI, that potential subject is withdrawn from the study. Should a subject recover neurological function and the SCI be deemed incomplete any time after the study drug has been administered, that participant will continue with all assessments and follow up studies without exception.

5. DXA Scan Analyses

Analyses of the distal femur and proximal tibia will be conducted as described by Modlesky⁷⁰⁻⁷⁴ and Shields⁷⁵. For the distal femur analysis, the distal edge of the DXA region of interest box will be placed at 13% of femur length and the proximal edge will be placed at 20% of femur length. For the proximal tibia, the same sized region of interest box will be placed immediately above the fibular head and extend distally (Figure 3).

Figure 3: DXA scans and region of interest for distal femur (A) and proximal tibia (B)

6. Safety Monitoring

Subjects will be interviewed daily for 3 days, then weekly for one month after study drug administration for any side effects of treatment, in particular, fever and myalgias, using a standardized interview form. Adverse events will be recorded and followed until resolution. A serious adverse event will constitute any event that is life-threatening, requires hospitalization, results in death or disability, requires intervention to prevent permanent impairment or damage, or results in a congenital anomaly. Important medical events that may not result in death, be life threatening or require hospitalization also may be considered to be a serious adverse event when, based on appropriate medical judgment, they may require medical or surgical intervention to prevent one of the outcomes listed in this definition. The PI will report all serious adverse events to the Safety Monitoring Board, the Jefferson IRB, and the project officer at NIDRR.

7. Data and Safety Monitoring Board (DSMB)

The DSMB will be recruited from Jefferson Medical College (JMC) faculty members and charged with monitoring study compliance. They will review screening and enrollment procedures, data collection and analysis, reporting of adverse events, and subject safety. The DSMB members will meet every 6 months or more frequently as needed. The study investigators will meet with the DSMB chair every 6 months to review recommendations or concerns.

The DSMB will be composed of the following members:

[name] [name] (Chair)	Professor of Rehabilitation Medicine
[name]	Assistant Professor of Medicine, Division of Endocrinology
[name]	Clinical Assistant Professor of Medicine, Division of Nephrology

E. Data Analysis

1. Evaluation of Baseline Characteristics

We will compare the treatment and control groups for baseline characteristics using t-tests and Chi-square tests as appropriate. Specifically, we will compare age at injury, baseline FRAX fracture risk, sex and injury level (tetraplegia/paraplegia) distribution. The level of significance for all analyses will be 0.05.

2. Evaluation of Hypotheses

Specific Aim 1: To determine the short and long term effects of zoledronic acid on BMD values of the hip, distal femur, and proximal tibia in patients with acute SCI relative to patients receiving placebo.

The primary hypothesis is that subjects treated with zoledronic acid will have at least a 50% smaller percentage decline in BMD values for the hip, distal femur and proximal tibia at 4 and 12 months post-injury than control subjects.

Analysis: For each of the bone sites to be evaluated, a percent change from baseline ([baseline BMD – follow-up BMD]/baseline BMD) will be modeled using mixed effects linear regression. Fixed effects will be included for treatment assignment, time, treatment by time interaction, and baseline BMD level. A random intercept term will be included to account for correlation among repeated measurements from the same subject. Within this regression model, we will estimate the difference between treatment groups at 4 and 12 months and test for significance of this difference. If the outcome of percent change is not normally distributed, we will apply an appropriate transformation (e.g., log, logit). If the necessary transformation is too complex for interpretation, we will consider using rank-based methods.

Secondary hypothesis 1 is that subjects treated with zoledronic acid will maintain original BMD values for the hip, distal femur and proximal tibia at 4 months and lose no more than 5% at 12 months post-injury.

Analysis: We will estimate the mean percent change at 4 and 12 months for the active treatment group along with associated 95% confidence intervals from the results of the mixed effects regression. BMD values at 4 months will be considered equivalent to those at baseline if the bounds of the confidence interval are within +/-2%. At 12 months, we will test the one-sided null hypothesis that the percentage decline is greater than 5% vs. the alternative that it is less than or equal to 5%.

Secondary hypothesis 2 is that fractures in the hip, distal femur, and proximal tibia will be at least 50% lower in the ZA group relative to controls over the course of the grant cycle. This final hypothesis is exploratory, since we do not expect to have the numbers to achieve statistical significance given the relatively low frequency of sublesional fractures in SCI.

Analysis: The relative risks of all fractures and site-specific fractures will be calculated along with exact 95% confidence intervals. Statistical significance will be evaluated using Fisher's exact test.

Specific Aim 2: To measure and compare levels of pro-osteoclastogenic factor IL-1 β , bone formation marker P1NP, and bone resorption marker serum C terminal telopeptide of type I collagen (s-CTX) in

acute traumatic motor complete SCI subjects who receive intravenous zoledronic acid in the first 21 days post injury to the same markers in a similar group of spinal cord injury subjects receiving placebo.

The primary hypothesis is that subjects treated with zoledronic acid will have lower levels of serum marker of bone resorption s-CTX at 4 and 12 months, relative to controls. In terms of absolute marker levels, we hypothesize that the ZA subjects will have s-CTX values within the reference range at 4 and 12 months, in contrast to control subjects whose resorption marker levels will be significantly above the reference range at all of the time points.

The secondary hypothesis is that levels of serum marker of bone formation PINP will not be lower than controls at 4 and 12 months.

Analysis: We will again use mixed effects linear regression to model each marker at 1, 4 and 12 months with fixed effects for time, treatment, time by treatment interaction, and baseline biomarker level and a random subject-specific intercept. At months 4 and 12, we will estimate mean group-specific biomarker levels and associated 95% confidence intervals and test for treatment group differences. Since IL-1 β will only be measured at baseline and one month, we will use analysis of covariance to compare group averages at one month adjusted for baseline measures.

Specific Aim 3: To determine the safety and tolerability of early administration of intravenous zoledronic acid in persons with acute SCI. We expect to see only minor, transient side effects from zoledronic acid. *To evaluate this we will test the hypotheses that compared to controls, subjects treated with zoledronic acid will have (3a) an increased incidence of myalgias, fever, gastrointestinal disturbances, and flu-like symptoms over the three days after infusion of study drug; (3b) be less likely to participate in physical and occupational therapy during the first week after infusion, and (3c) be less likely to want the treatment again.*

Analysis: For each outcome, we will estimate group-specific rates (proportions) along with exact binomial confidence intervals. Comparisons between groups will be performed using Fisher's exact test.

References Cited

1. National Institute on Disability and Rehabilitation Research. Notice of Final Long-Range Plan for Fiscal Years 2005-2009. *Federal Register*. 2006;71(31):8166-8200.

8. Ashe MC. Bone Health Following Spinal Cord Injury. *Spinal Cord Injury Rehabilitation Evidence*. Ed. J. J. Eng et al. 2010. 1-26.

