Due to the potency of IV ZA, adverse effects of the agent may occur. The most common side effects of ZA are an acute phase reaction involving fever (15%), myalgias (8%), flu-like illness (7%), headache (6%) and arthralgias (5%)^{61,62}. In rare cases, patients may experience noncardiac chest pain (1/3%). Because infusion of IV ZA can cause an increase in serum creatinine up to 30 days post treatment, the drug should be avoided in persons with creatinine clearance <35 mL/min. An association between atrial fibrillation and IV ZA use was observed in a large study of over 7000 patients⁶². The FDA subsequently conducted an investigation, comparing results of the prior trial to other studies of IV ZA, and concluded that no clear relationship could be identified between bisphosphonate use and atrial fibrillation⁶³. Both oral and IV bisphosphonates have been associated with osteonecrosis of the jaw (ONJ), but further review of the data by the American Dental Association found that incidence of ONJ is rare in post-menopausal women with osteoporosis but more common in those with monthly infusions for cancer treatment⁶⁴. This group recommended no special treatment beyond routine dental care for those using IV ZA for osteoporosis. Finally, several reports of low trauma fractures of the femur have been observed among patients primarily over age 60 who are prescribed chronic bisphosphonate treatment (2.5-8 years)^{61,65}. A recent cohort study of over 1.1 million patients by Dell et al. found that while duration of use of bisphosphonates was correlated with incidence of atypical femur fractures, (particularly beyond 5 years of use), no correlation with age and duration of use was found.⁶⁶ Because our study will involve only a single dose of ZA, we do not anticipate observing the above effect from the drug alone. Based on these new findings, we also believe that individuals ages 61-65 should not be excluded by age alone.

Previous Clinical Trials of Zoledronic Acid

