This study will be conducted at the Regional Spinal Cord Injury Center of the Delaware Valley (RSCICDV), located at Thomas Jefferson University and Hospital (TJU/H) in Philadelphia, PA. TJUH, in affiliation with the Magee Rehabilitation Hospital, is designated as one of the United States' 16 Model Spinal Cord Injury Centers, by the National Institute on Disability and Rehabilitation Research, Department of Education's Office of Special Education and Rehabilitative Services. It is the only such facility in the Delaware Valley. The RSCIC has treated more than 3,000 persons with spinal cord injury and provides for multidisciplinary coordination of emergency and acute medical/surgical care, rehabilitation at the onset of acute care, with vocational evaluation and training, and lifetime follow-up care for persons with SCI. Over 50 percent of the SCI patient population is admitted to the RSCIC within three days of injury and the RSCIC has demonstrated a mortality rate of 5 percent. Over the past 5 years the RSCIC has annually admitted an average of 28-30 patients with complete SCI within 7 days of injury.

D.1. Subjects

Forty-eight subjects evaluated to have ASIA impairment scale Grade A injuries (motor and sensory complete) will be identified, screened, and approached to participate in the study. Persons who have recently experienced traumatic complete SCI and are within 21 days of injury are eligible to participate. The sample size calculation allows for reduced enrollment rates and drop outs. The ASIA impairment scale is detailed in **Table 3** below.

Table 3: ASIA Impairment Scale (ISNCSCI, 2011)

SCI Injury Grade	Description
A = Complete	No motor or sensory function is preserved in the sacral segments S4-S5.
B = Incomplete	Sensory but not motor function is preserved below the neurological level and includes the sacral segments S4-S5.
C = Incomplete	Motor function is preserved below the neurological level, and more than half of key muscles below the neurological level have a muscle grade less than 3.
D = Incomplete:	Motor function is preserved below the neurological level, and at least half of key muscles below the neurological level have a muscle grade of 3 or more.
E = Normal	Motor and sensory functions are normal.

D.2. Inclusion/Exclusion Criteria

Inclusion criteria:

- Ages 18- 65, male or female
- Traumatic SCI with Neurological level C4-T10, AIS A, Serum calcium level >7.0 mg/dL) at time of study drug administration

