- Screening baseline serum 25OH vitamin D of at least 13 ng/ml
- No medical contraindication to supplemental vitamin D for participants whose levels are >13 ng/ml but sub-therapeutic (<32ng/ml)
- No medical contraindication to supplemental calcium
- Weight under 300 pounds, which is the maximum permitted on the DXA scanner

Exclusion criteria:

- Ventilator dependent individuals who are not in weaning phase and are unable to provide consent through alternative communication
- Chronic steroid use (defined as >6 months)
- Rheumatoid disease with use of prior disease modifying anti-rheumatic drugs (DMARDs) affecting bone density
- History of osteoporosis or of treatment for osteopenia or osteoporosis with bisphosphonates, or selective reuptake estrogen modifying agents
- Current use of medications* including bisphosphonates to treat osteoporosis (*note that prior calcium or vitamin D use is not an exclusion criteria)
- History of more than one lower extremity osteoporosis-related fracture
- Chronic renal insufficiency, creatinine clearance < 35 ml/min, during screening
- End stage liver or kidney disease
- Medical conditions resulting in hypogonadal states that affect bone density
- Uncontrolled thyroid disease/thyroiditis
- Hereditary or acquired metabolic bone disorder
- History of use of unfractionated heparin for >1 year
- History of selected antiseizure medications, specifically phenobarbital, phenytoin, carbamazepine, sodium valproate >1 year
- Acute or chronic bilateral lower extremity fractures involving tibia or femur, with placement of surgical hardware in any areas of above locations
- Severe hypotension requiring use of IV blood pressure agents such as dopamine, norepinephrine, or phenylephrine. Exception may allow for patients on pressors who are experiencing hypotension as they acclimate to upright posture
- Inability to provide informed consent and understand the consent process
- Facial fractures requiring oral surgery

- Dental surgery or oral maxillofacial surgery within 2 weeks of anticipated study drug administration
- Pregnancy present on admission
- Vitamin D deficiency on admission testing (serum 25-OH D reported as < 13 ng/mL)
- Patients with an established reaction to, or history of, anaphylactic shock to aspirin

D.3. Methods

1. Sample Size Calculations

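### Creatinine clearance is checked only at screening, and no creatinine is scheduled at or after infusion, although the plan says the drug can raise creatinine for up to 30 days

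*Combined protocol and SAP*

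**What the plan says.** Section C (Side Effects of Zoledronic Acid) names the hazard, "infusion of IV ZA can cause an increase in serum creatinine up to 30 days post treatment", and gives it as the reason to avoid the drug when clearance is below 35 mL/min. Section D.2 turns this into an exclusion: "creatinine clearance < 35 ml/min, during screening". Under D.3, item 4, A (Screening), the standard-care metabolic and hepatic panels are reviewed on days 0-17 to rule out an unrecognised history of chronic kidney or liver failure. Table 4 marks the panel in the screening column only.

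Two other entry conditions are checked again close to dosing. The calcium criterion in D.2 applies "at time of study drug administration", and the infusion visit (D.3, item 4, C) includes "Measurement of serum calcium level to ensure therapeutic levels". For completeness of injury, the section on physical examinations states: "A confirmatory exam will be conducted in the 24 hours prior to study drug delivery".

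For days 1, 3, 7 and 14 after infusion (D.3, item 4, E) the instruction is "Laboratory values will be drawn for serum calcium, phosphate, and magnesium". Side effects are sought by interview, daily for three days and then weekly for a month (D.3, item 6). Specific Aim 3 (section E.2) compares symptoms over three days, participation in therapy, and willingness to be treated again.

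**The concern.** The plan gives a reason to withhold the drug, ties it to a number, and then checks that number once, at a visit that can precede dosing by up to three weeks in acutely injured patients. Calcium and injury grade are rechecked before dosing; clearance is not. This part carries a decision, to dose or not to dose.

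The second part is follow-up. Aim 3 sets out to determine the safety of early zoledronic acid, given sooner after injury than in the earlier studies of the drug in spinal cord injury. A creatinine rise without symptoms cannot be found by interview. Without a scheduled value, the trial has no planned data by arm on a laboratory harm that it links to the drug itself.

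**Working it through.** **1. Inventory of scheduled tests** (D.3, item 4, with Table 4)

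| Time | Main tests | Creatinine or metabolic panel |
|---|---|---|
| Screening, days 0-17 after injury | Metabolic and hepatic panels, calcium, vitamin D, iPTH | Yes |
| Baseline, days 8-21 | P1NP, s-CTX, IL-1β, CPK, calcium | No |
| Infusion, by day 21 | Calcium | No |
| Days 1, 3, 7, 14 after infusion | Calcium, phosphate, magnesium | No |
| Month 1 after injury | s-CTX, IL-1β, vitamin D, calcium, iPTH, P1NP | No |
| Month 4 | s-CTX, vitamin D, calcium, iPTH, P1NP | No |
| Month 8 | Vitamin D, calcium | No |
| Month 12 | s-CTX, vitamin D, calcium, iPTH | No |

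Count: one before infusion, none at or after it. Table 4 has no day 1-14 columns, so for those days the visit text is the evidence.

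**2. Age of the clearance at dosing.** Age = infusion day minus screening day.
- Infusion on day 21, screening on days 0-17: 21 - 17 = 4 to 21 - 0 = 21 days.
- Infusion on day 8 (assumed earliest, because baseline assessments start then): at most 8 - 0 = 8 days.
- The baseline blood sample would not be a safe substitute for a test at infusion: drawn on day 8 for a day-21 infusion, it is 21 - 8 = 13 days old.

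**3. How far the existing draws reach into the 30-day window.** Month 1 is counted from injury. Taking it as day 30 ± 4, that is days 26-34:
- Infusion on day 8: 26 - 8 = 18 to 34 - 8 = 26 days after infusion.
- Infusion on day 21: 26 - 21 = 5 to 34 - 21 = 13 days after infusion, so the day-14 draw is then the last in the window.

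The existing draws therefore cover most of the window for early dosing and about half for late dosing. None reaches day 30.

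**4. What post-dose values could show.** Allocation 2:1 of 48 gives 32 on zoledronic acid and 16 on placebo. The plan states no rate for a creatinine rise, so there is no figure of its own to reproduce, and the rates below are assumptions.
- Chance of at least one case among 32, if each is measured while the rise is present: 1 - 0.95^32 = 81% at a true rate of 5%; 1 - 0.90^32 = 97% at 10%.
- Exact two-sided 95% upper limit after zero cases: 1 - 0.025^(1/32) = 10.9%. If only 24 are measured (assumed 75%): 1 - 0.025^(1/24) = 14.2%.
- Power of Fisher's exact test, two-sided 0.05, 32 versus 16: 1.0% for 10% versus 1%; 23% for 20% versus 2%; 66% for 30% versus 2%.

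Post-dose measurement can find individual cases and describe the arms. It cannot support a formal comparison unless the difference is very large.

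**The case against.** The strongest reply is that the plan already acts on the risk. It excludes low clearance and end-stage kidney disease, infuses over two hours, supports urine output until day 3, follows adverse events to resolution, and has a nephrologist on the DSMB. These measures reduce risk and deserve credit. None is a measurement of creatinine, and the hydration covers only the first three days of a 30-day window.

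Several stronger readings are tempting, and the documents do not support them.
- A reader might infer that the screening panel is the only kidney-related test. The baseline assessments include CPK and describe it as reflecting kidney function as well as muscle. It is a single pre-treatment value and does not give clearance, so the gap remains, but the accurate statement concerns creatinine and the metabolic panel.
- A reader might infer that a rise would go unseen, or be found only by luck. The panel is labelled standard care, and the subjects are acutely injured patients recruited soon after admission. The documents do not say how often it is repeated. They support only that the protocol neither requires nor collects later values.
- A reader might infer that everyone is dosed on a three-week-old result. Twenty-one days is the extreme for dosing on day 21; the usual dosing day is not given.
- A reader might take the missing comparison between arms as the main loss. The power figures show how little a test would offer.

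It can also be said that, since a single infusion cannot be withdrawn, post-dose values change less than a pre-dose check. That stands, and it is why the pre-dose check comes first. Post-dose values help a subject only if the plan also says what counts as a rise and what follows.

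**Conclusion.** The point holds as a gap in safety assessment with a cheap remedy. No creatinine is scheduled at or after infusion for any of the 48 subjects, and the clearance that governs dosing can be 4 to 21 days old for a day-21 infusion, or at most 8 days for a day-8 infusion. The conclusion rests on the visit lists and Table 4. The ages also assume that the screening panel may fall on any day of its window. Whether hospital practice closes the gap is not stated. The gain from the change is protection of individual subjects and a descriptive account of a harm that the plan names. The BMD and biomarker analyses in Aims 1 and 2 are not touched.

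**What to change.** **First, before dosing.** Add serum creatinine to the calcium measurement at the infusion visit (D.3, item 4, C) and require clearance of at least 35 mL/min before the drug is given. Where possible, have the result before the pharmacy service assigns the randomization, so that a failed check does not leave a randomized subject undosed.

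**Second, after dosing.** Add creatinine to the existing day 1, 3, 7, 14 and month-1 draws (D.3, item 4, E and F), with a row and a footnote in Table 4. Pre-specify the size of rise that triggers a repeat test, clinical review and adverse event recording. The documents give no threshold, so the investigators should set one, for example with the DSMB's nephrology member. In Aim 3, report change from the pre-dose value by arm, with the number measured at each time and no significance test, and include it in the DSMB reports. One further draw near day 30 after infusion is optional and would complete the window.

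**Cost.** Up to six routine assays per subject, 6 × 48 = 288 at most, on samples already planned and with no added visit. The pre-infusion result must be back before dosing, which may delay or exclude a subject whose clearance has fallen. A short rule for handling rises has to be written, with small edits to the visit text, Table 4 and the Aim 3 analysis. The optional day-30 test is one extra blood draw per subject.
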